3.5.2.2. Systemic Events

Prior to vaccination on Day 1, a baseline assessment of fatigue, headache, vomiting, nausea, diarrhea, muscle pain, and joint pain will be recorded in the e-diary. Systemic events reported for Days 1 to 7 following vaccination via the e-diary are fever, fatigue, headache, vomiting, nausea, diarrhea, muscle pain, and joint pain. The participant or her parent(s)/legal guardian (if a minor) is to document the presence or absence of systemic events in the e-diary as “mild,” “moderate,” “severe,” or “none”. Participants are to be asked to assess the severity of each event according to [Table 5](#).

Only an investigator is able to classify a maternal participant’s systemic event as Grade 4, after clinical evaluation of the maternal participant or documentation from another medically qualified source (eg, emergency room or hospital record) or contact with the participant. If a maternal participant experiences a Grade 4 systemic event, the investigator must immediately notify the sponsor. A Grade 4 event will be collected on the unscheduled reactogenicity page and as an AE on the CRF. The event will be graded using the AE severity grading scale (see [Section 10.2.4 of the protocol](#)). Further, for all ongoing systemic events on Day 7, the stop date will be recorded in the CRF.

Table 5. Grading Scale for Systemic Events

	Mild Grade 1	Moderate Grade 2	Severe Grade 3	Grade 4^a
Fatigue (= tiredness in diaries)	Does not interfere with activity	Some interference with activity	Prevents daily routine activity	Emergency room visit or hospitalization for severe fatigue
Headache	Does not interfere with activity	Some interference with activity	Prevents daily routine activity	Emergency room visit or hospitalization for severe headache
Vomiting	1 to 2 times in 24 hours	>2 times in 24 hours	Requires intravenous hydration	Emergency room visit or hospitalization for severe vomiting
Nausea	Does not interfere with activity	Some interference with activity	Prevents daily routine activity	Emergency room visit or hospitalization for severe nausea
Diarrhea	2 to 3 loose stools in 24 hours	4 to 5 loose stools in 24 hours	6 or more loose stools in 24 hours	Emergency room visit or hospitalization for severe diarrhea
Muscle pain	Does not interfere with activity	Some interference with activity	Prevents daily routine activity	Emergency room visit or hospitalization for severe muscle pain
Joint pain	Does not interfere with activity	Some interference with activity	Prevents daily routine activity	Emergency room visit or hospitalization for severe joint pain

a. Only an investigator is able to classify a maternal participant's systemic event as Grade 4, after clinical evaluation of the maternal participant or documentation from another medically qualified source (eg, emergency room or hospital record) or contact with the maternal participant or her parent(s)/legal guardian (if a minor). Grade 4 assessment should be made by the investigator using the AE severity grading scale. The assessment will be collected on the AE case report form.

The highest temperature for each day for 7 days after vaccination is to be recorded in the e-diary. The protocol defines fever as an oral temperature $\geq 38.0^{\circ}\text{C}$ ($\geq 100.4^{\circ}\text{F}$). For ongoing fever on Day 7, the stop date will be recorded in the CRF. Any temperatures recorded as $<35.0^{\circ}\text{C}$ or $>42.0^{\circ}\text{C}$ will be treated as data-entry errors and excluded from the analyses. For reporting purposes, fever will be analyzed using the temperature grading scale displayed in Table 6.

Table 6. Grading Scale for Fever

Mild Grade 1	Moderate Grade 2	Severe Grade 3	Grade 4^a
$\geq 38.0^{\circ}\text{C}$ to 38.4°C	$>38.4^{\circ}\text{C}$ to 38.9°C	$>38.9^{\circ}\text{C}$ to 40.0°C	$>40.0^{\circ}\text{C}$

a. Only an investigator or qualified designee is able to classify a maternal participant's fever as Grade 4, after clinical evaluation of the maternal participant, documentation from another medically qualified source (eg, emergency room or hospital record), or contact with the maternal participant or her parent(s)/legal guardian (if a minor). Grade 4 fevers will be collected on the AE CRF and assessed by the investigator using the AE intensity grading scale as detailed in [Section 10.2.4 of the protocol](#).

The presence or absence of each systemic event on a given day is defined as follows:

- = “Missing,” if the value is missing on a given day.
- = “Yes,” if a temperature $\geq 38.0^{\circ}\text{C}$ for fever **or** “mild,” “moderate,” “severe,” or “Grade 4” for the remaining events are reported on a given day.
- = “No,” if a temperature $< 38.0^{\circ}\text{C}$ for fever **or** “none” for the remaining events are reported on a given day.

For each systemic event, the following variables will be derived:

1. Presence or absence of each systemic event on each day (Days 1-7) after vaccination.
2. Presence or absence of each systemic event on “any day (Day 1-7)” after vaccination.
3. Presence or absence of any systemic event on “any day (Day 1-7)” after vaccination.
4. Maximum severity of each systemic event on “any day (Day 1-7)” after vaccination.
5. Duration of each systemic event after vaccination.
6. Onset day of each systemic event after vaccination.
7. Onset day of any systemic event after vaccination.

The derivation of these variables is similar to the derivation of the variables for local reactions (Section 3.5.2.1). “Any systemic event” includes any fever, fatigue, headache, vomiting, nausea, diarrhea, muscle pain, or joint pain.

3.5.3. Physical Examination, Including Vital Signs

3.5.3.1. Physical Examination, Including Vital Signs: Maternal Participants

Physical examination will be performed at the screening visit and will include any clinically significant abnormalities within the following body systems: general appearance; skin; head, eyes, ears, nose, and throat; heart; lungs; abdomen; musculoskeletal; extremities; neurological; and lymph nodes. Height and weight will also be measured and recorded.

Vital signs including sitting systolic and diastolic blood pressure, heart rate, and oral temperature will be measured at the screening visit and recorded in the CRF.

3.5.3.2. Physical Examination, Including Vital Signs: Infant Participants

The physical examination will be performed at all scheduled in-clinic visits and will include any clinically significant abnormalities within the following body systems: general appearance; skin; head, eyes, ears, nose, and throat; heart; lungs; abdomen; back; musculoskeletal; extremities; genitourinary; neurological; and lymph nodes.

Length, head circumference, and weight will also be measured and recorded.

Temperature, heart rate, and respiratory rate as well as oxygen saturation by pulse oximetry will be assessed at birth, at 1 month of age, and during the active RSV surveillance procedures.

3.5.4. Obstetric Examination

Obstetric history and examination findings will be collected at the vaccination visit. The assessments will include, but not be limited to, number of pregnancies, cesarean deliveries, spontaneous abortions, ectopic pregnancies, number of preterm deliveries, GA at vaccination, and fetal movement.

The following information regarding pregnancy outcome will be collected: date of delivery, location of delivery (medical facility, home, other), mode of delivery (vaginal, cesarean delivery), cesarean type (elective, semielective, emergency), the use of any assisted devices (forceps or vacuum), delivery complications (yes, no), number of births, outcome at delivery (live delivery, stillbirth, induced/elective abortion), gross visual inspection of the aborted fetus/stillbirth (not done, no observed abnormalities, observed abnormalities), and fetal pathology performed (yes, no). In addition, if information is available, group B streptococcal colonization status will also be collected along with any intrapartum antibiotic prophylaxis.

3.5.5. Birth Outcome: Infant Participants

Infant outcome at birth will be collected at the delivery visit and includes the following: GA (weeks, days); Apgar score at 1, 5, and 10 minutes; infant cry immediately after delivery (yes, no); infant suckle shortly after delivery (yes, no); and infant outcome (normal, congenital malformation/anomaly, other neonatal problem or unknown). Neonatal death will be derived using the response to “delivery outcome” from the pregnancy outcome and the AE data. Neonatal death is defined as the death of a live-born infant that occurred within a month (30 days) after birth.

3.6. Health Economics

3.6.1. Healthcare Resource Utilization: Infant Participants

Details of healthcare resource utilization for all infants will be assessed at each MA-RTI visit from 72 hours after birth through the last study visit (730 days after birth). The variables collected will include the following: number, type (eg, respiratory, RAD/asthma/wheezing), and setting (eg, outpatient, urgent care, emergency room, hospitalization, ICU) of healthcare visits, length of hospital stay, requirement for mechanical ventilation (yes/no, total number of mechanical ventilation episodes, total number of hours/days on mechanical ventilation), requirement for respiratory diagnostic procedures (eg, chest radiograph, supplemental oxygen, pulse oximetry), requirement for IV fluids, requirement for prescriptions (eg, total number of prescriptions, selected respiratory medications [eg, bronchodilators, corticosteroid therapy, racemic epinephrine]), and antibiotic use (eg, total number of prescriptions, number of antibiotic use days).

4. ANALYSIS SETS (POPULATIONS FOR ANALYSIS)

Data for all participants will be assessed to determine if participants meet the criteria for inclusion in each analysis population prior to unblinding and releasing the database and classifications will be documented per standard operating procedures.

Population	Description
Enrolled	All participants who sign the informed consent document.
Randomly assigned to investigational product	All maternal participants who are assigned a randomization number in the IRT system.
Evaluable efficacy – infant (per-protocol)	All infant participants who are born to maternal participants who did not have major protocol deviations prior to the delivery and who received the investigational product to which they were randomized at least 14 days prior to delivery, are eligible, and have no major protocol deviations.
ITT efficacy – infant	All infant participants who are born to vaccinated maternal participants.
Evaluable immunogenicity – infant	All infant participants who are born to maternal participants who did not have major protocol deviations prior to the delivery and who received the investigational product to which they were randomized, are eligible, have blood drawn for assay testing within the specified time frame, ^a have valid and determinate assay results for the proposed analysis, and have no major protocol deviations.
Evaluable immunogenicity – maternal	All maternal participants who are eligible, receive the investigational product to which they were randomized, have blood drawn for assay testing within the specified time frame, ^b have valid and determinate assay results for the proposed analysis, and have no major protocol deviations.
ITT immunogenicity – infant	All infant participants who are born to vaccinated maternal participants and have at least 1 valid and determinate assay result for the proposed analysis.
ITT immunogenicity – maternal	All randomized maternal participants who receive investigational product and have at least 1 valid and determinate assay result for the proposed analysis.
Safety – infant	All infant participants who are born to vaccinated maternal participants.
Safety – maternal	All randomized maternal participants who receive investigational product.

- a. A cord blood sample must be obtained on the day of birth. If cord blood is unavailable, a venous blood sample may be collected from the infant preferably within 24 hours but up to 7 days after birth.
- b. The blood sample must be obtained preferably before the delivery. In the event that the blood sample cannot be obtained before delivery, the sample should be collected as close to delivery as possible and at most 48 hours postpartum.

Major protocol deviations will be determined by clinical review and identified before any immunogenicity or efficacy analysis is carried out. A major protocol deviation is a protocol violation that, in the opinion of the study clinician medical monitor, would materially affect assessment of immunogenicity or efficacy, eg, participant receipt of a prohibited vaccine or medication that might affect immune response or a medication error with suspected decrease in potency of the vaccine.

[figure not shown]

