2.1.4. Primary Estimands

2.1.4.1. Primary Efficacy Estimands – Infant Participants

- **VE, defined as the RR reduction of RSV-positive MA-LRTI occurring within 90 days, 120 days, 150 days, and 180 days after birth in the RSV vaccine group compared to the placebo group.**

This estimand includes the following 4 attributes:

- Population: Infant participants born to maternal participants receiving 1 dose of investigational product and in compliance with the key protocol criteria (evaluable efficacy infant participants).
- Variable: Occurrence of RSV-positive MA-LRTI within 90 days, 120 days, 150 days, and 180 days after birth as confirmed by the EAC (any adjudicated severe MA-LRTI cases due to RSV are also by definition MA-LRTI cases).
- Intercurrent event(s): For participants who discontinue from the study or have major protocol deviations, all postdiscontinuation or postviolation observations will be censored; such events include the infant receiving palivizumab or another monoclonal antibody targeting RSV and the infant receiving transfusions of more than 20 mL/kg of any blood products at ≤ 180 days of age.
- Population-level summary: RR reduction of RSV-positive MA-LRTI occurring up to 90 days, 120 days, 150 days, and 180 days in the RSV vaccine group compared to the placebo group.

- **VE, defined as the RR reduction of severe MA-LRTI due to RSV occurring within 90 days, 120 days, 150 days, and 180 days after birth in the RSV vaccine group compared to the placebo group.**

This estimand includes the following 4 attributes:

- Population: Infant participants born to maternal participants receiving 1 dose of investigational product and in compliance with the key protocol criteria (evaluable efficacy infant participants).
- Variable: Occurrence of severe MA-LRTI due to RSV occurring within 90 days, 120 days, 150 days, and 180 days after birth as confirmed by the EAC.
- Intercurrent event(s): For participants who discontinue from the study or have major protocol deviations, all postdiscontinuation or postviolation observations will be censored; such events include the infant receiving palivizumab or another monoclonal antibody targeting RSV and the infant receiving transfusions of more than 20 mL/kg of any blood products at ≤ 180 days of age.
- Population-level summary: RR reduction of severe MA-LRTI due to RSV occurring up to 90 days, 120 days, 150 days, and 180 days in the RSV vaccine group compared to the placebo group.

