6.1.1.1.1. Main Analysis

- Estimand strategy: Hypothetical.
- Analysis set: Evaluable efficacy – infant ([Section 4](#)).
- Analysis methodology: VE will be analyzed using a conditional exact test based on the binomial distribution of the number of disease cases in the RSV vaccine group, given the total number of cases in both groups.
- Intercurrent events and missing data: All postdiscontinuation or postviolation observations will be censored; such events include the infant receiving palivizumab or another monoclonal antibody targeting RSV and the infant receiving transfusions of more than 20 mL/kg of any blood products at ≤ 180 days of age.
- For each group, the number (n), percentage, and 95% CI of RSV-positive MA-LRTI cases occurring within 90 days, 120 days, 150 days, and 180 days after birth, as confirmed by the EAC, will be presented for each group. Severe MA-LRTI cases are a subset of MA-LRTI cases, and all severe MA-LRTI cases will also be considered MA-LRTI cases.

- VE compared to placebo along with the corresponding 100(1- alpha)% CI (adjusted for the interim) will be presented. This will be based on raw numbers of cases and also with an adjustment for any differences in follow-up time. See [Section 5.1](#) for testing procedures.
- Kaplan-Meier curves showing accrual of cases for this endpoint over 180 days will be presented.

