6.3.1.2. RSV-Positive MA-RTI Occurring 181 to 730 Days After Birth

- Analysis set: Evaluable efficacy – infant ([Section 4](#)).
- Analysis methodology: VE will be analyzed using a conditional exact test based on the binomial distribution of the number of disease cases in the RSV vaccine group, given the total number of cases in both groups. Events that happen after the infant received palivizumab or another monoclonal antibody targeting RSV or after he/she had transfusions of more than 20 mL/kg of any blood products at ≤ 180 days of age will be excluded.
- For each group, the number (n), percentage, and 95% CI of RSV-positive MA-RTI cases occurring within 181 to 730 days will be presented for each group.
- For each group, the number (n), percentage, and 95% CI of RSV-positive MA-RTI cases occurring within 361 to 730 days will be presented for each group (just for the participants enrolled in the first year of the study).
- VE compared to placebo along with the 95% CI will be presented for each analysis interval separately.

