7.2. Interim Analyses and Summaries

Interim analyses may be performed to assess efficacy and safety after at least 43 cases of MA-LRTI-due-to-RSV within 90 days have occurred.

Based on the fraction of cases included in an interim analysis, an alpha level will be derived based on a Lan-DeMets implementation of the O'Brien-Fleming alpha spending function. For example, a first interim analysis at 43 cases would use a 1-sided significance level of 0.014%. If a second interim analysis were performed, for example at 62 cases, it would use a 1-sided significance level of 0.15%. The final analysis at the target number of cases would use a 1-sided significance level of 2.45%. Implementation of these 1-sided significance levels ensures that the overall type I error for the primary endpoint will be no more than 0.025. The alpha levels used at interim and final analyses will depend on the exact fraction of cases available at the interim analysis. The exact number of cases at each interim analysis is not fixed and may be decided based on operational reasons. However, no fewer than 43 cases will be included in the first interim analysis and no fewer than 62 cases will be included in the second interim analysis.

The order of cases included in the interim analysis will be determined by the EAC as those first confirmed to meet the protocol-defined criteria. When the target number of cases for an interim analysis is reached, it is possible that additional potential cases will be under adjudication. Only cases that have been fully adjudicated up to the day of data snapshot will be included in an interim analysis.

Consideration will be given to stopping the study for efficacy if the analysis of either primary endpoint through 90 days indicates statistically significant efficacy. Secondary endpoints will not be tested at the interim analysis.

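### The evaluable efficacy infant set excludes infants with a major protocol deviation without a time limit, while the estimands for that set only censor observations after the deviation; Section 4 was not aligned

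*SAP*

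**What the plan says.** **Set membership (SAP Section 4).** The evaluable efficacy infant set has a maternal condition and an infant condition. The mother must have had no major deviation before delivery and must have "received the investigational product to which they were randomized at least 14 days prior to delivery, are eligible, and have no major protocol deviations". The closing words apply to the infant and, unlike the maternal condition, name no period.

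**Estimand (SAP Section 2.1.4.1).** The population is infants "in compliance with the key protocol criteria (evaluable efficacy infant participants"), which is the Section 4 set. The intercurrent-event rule reads: "For participants who discontinue from the study or have major protocol deviations, all postdiscontinuation or postviolation observations will be censored". Receipt of palivizumab or another RSV monoclonal antibody, and transfusion above 20 mL/kg at up to 180 days of age, are then given as included examples. Section 2.1.5.1 repeats the rule for every secondary efficacy estimand.

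**Main analyses.** Section 6.1.1.1.1 names the evaluable efficacy infant set and says: "All postdiscontinuation or postviolation observations will be censored". Sections 6.1.1.2.1, 6.2.1.1.1 and 6.2.1.3.1 do the same, and 6.2.1.2 follows 6.2.1.1 by reference. On the efficacy estimate, 6.1.1.1.1 adds: "This will be based on raw numbers of cases and also with an adjustment for any differences in follow-up time".

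**What a major deviation is (SAP Section 4, text after the table).** It is a matter for the medical monitor's opinion, with "participant receipt of a prohibited vaccine or medication that might affect immune response" as one example. The text does not divide deviations into those that exclude and those that censor.

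**The concern.** The two rules treat the same infant differently. Take an infant with a committee-confirmed RSV MA-LRTI who later has a major deviation. Under the censoring rule the case counts and the infant contributes follow-up up to the deviation. Under the untimed exclusion the infant is not in the set, and both the case and the follow-up are lost.

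Three quantities depend on the choice: the primary case counts, the follow-up time behind the adjusted efficacy estimate, and the count toward the 124 per-protocol cases in Section 2.2. The exclusion also conditions membership on something that happens after birth, and possibly after the endpoint, which is not the hypothetical estimand that Section 6.1.1.1.1 declares.

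There is a consequence for interim looks too. Section 7.2 says "no fewer than 43 cases will be included in the first interim analysis", while infants are still being followed. A case counted then could in principle leave the set later under the exclusion rule, but not under censoring.

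**Working it through.** **1. The rules side by side**

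| | Section 4 | Sections 2.1.4.1, 2.1.5.1 and the main analyses |
|---|---|---|
| Set | Evaluable efficacy – infant | The same |
| Mother's major deviation | Excludes, if before delivery | Not addressed separately |
| Infant's major deviation | Excludes, no period given | Infant stays; later observations censored |
| Confirmed case before the deviation | Lost | Counted |
| Follow-up before the deviation | Lost | Counted |

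If the infant clause is applied as written, no infant with a major deviation remains in the set, and the censoring rule has no infant deviation to act on. If the censoring rule is applied as written, the infant clause is too broad. Both cannot hold.

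**2. Which way the rest of the SAP points**

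The censoring rule is worded for major deviations in general, and the antibody and transfusion events are only examples. The version 4 entry in Table 1 records that those two events were taken out of the set definition so as to become endpoint-specific. Both favour censoring. The log covers only the two named events, and the current Section 4 has no wording that makes room for either.

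**3. How much a single case can matter**

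The SAP states no figure that depends on this point, so this is a check of size only. Inputs:
- Null VE ≤ 20% (Section 5.1), so π₀ = (1 − 0.20)/(2 − 0.20) = 0.8/1.8 = 0.4444 (formula in Section 5.2.1, which assumes equal group sizes).
- Target of 124 cases (Section 2.2), taken as the number in the window tested.
- Final 1-sided level 2.45% (the Section 7.2 example), halved for two primary endpoints: 0.0245/2 = 0.01225.
- VE = 1 − vaccine cases/placebo cases; p = P(X ≤ vaccine cases) for a binomial with the total number of cases and π₀.

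The same test gives the efficacy limits in Table 11: at most 6 vaccine cases of 43 (p = 0.00002 against 0.00014/2 = 0.00007; 7 cases give 0.00009) and at most 14 of 62 (p = 0.00029 against 0.0015/2 = 0.00075; 15 cases give 0.00078).

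| Situation | Vaccine / placebo | VE | 1-sided p | Rejects at 0.01225 |
|---|---|---|---|---|
| Near the 60% design value | 35 / 89 | 60.7% | 0.00015 | Yes |
| One vaccine case lost | 34 / 89 | 61.8% | 0.00009 | Yes |
| One placebo case lost | 35 / 88 | 60.2% | 0.00020 | Yes |
| Final boundary | 42 / 82 | 48.8% | 0.0107 | Yes |
| Boundary, one vaccine case lost | 41 / 82 | 50.0% | 0.0079 | Yes |
| Boundary, one placebo case lost | 42 / 81 | 48.1% | 0.0130 | No |

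The rule decides the result only in the last row. With true VE 60% (π = 0.4/1.4), the probability of exactly 42 vaccine cases of 124 is about 3%, before asking that a placebo case also be followed by a major deviation.

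**4. How many cases could differ**

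The SAP gives no rate of postnatal deviations. Assumption only: if 0.5%, 1% or 2% of 124 cases were in infants with a later major deviation, the counts would differ by 0.62, 1.24 or 2.48 cases.

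**The case against.** The strongest reply is that the SAP can be harmonised: Section 4 governs entry to the set, and later deviations are intercurrent events under the estimand. The estimand rule is the more specific one, is repeated at every primary and secondary efficacy endpoint, and would be idle otherwise. This stands as evidence of intent. A reader might infer that nothing in the SAP indicates which rule applies; that goes too far. What remains is that Section 4, which defines the set, says something else.

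A second reply is that few deviations are affected. Only mothers are vaccinated, so the immune-response example fits them best, and the obvious infant events are already named for censoring. That is fair. The definition still does not confine major deviations to mothers or to the time before birth, so the group is open, though perhaps small.

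Third, Section 4 requires that a deviation materially affect the assessment of immunogenicity or efficacy, and that it be identified before any such analysis. The set also serves late endpoints (Section 6.3.1.2: "RSV-positive MA-RTI cases occurring within 181 to 730 days will be presented for each group"), so a reader might picture an event at day 300 removing a day-40 case. The materiality condition makes that example weak for a 90-day endpoint, and follow-up to 730 days applies only to infants of mothers enrolled in the first year.

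Finally, classification before unblinding and the repeat in the mITT population limit the harm. Neither says which per-protocol count is primary.

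**Conclusion.** The inconsistency is real and should be fixed. Followed exactly, Section 4 gives a different primary case count and follow-up time from the SAP's own estimand whenever an infant has a case and then a major deviation. That Section 4 excludes for deviations at any time is the plain reading of an untimed clause, not its own words.

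The effect is probably small and cannot be estimated from the SAP. A reader might infer that the primary conclusion is at risk; the figures do not support that. Near 60% efficacy no decision changes, and one lost infant matters only at the exact final boundary and only if the lost case is in the placebo group. This rests on 124 cases in the tested window, equal groups and the example final level of 2.45%. No stated alpha level or Table 11 figure is affected. Protocol Section 9.2, which Section 2.2 cites for this population, was not available and may settle the timing; the SAP text would still need to agree with it.

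**What to change.** Before unblinding, align Section 4 with the estimand:

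- Limit the infant exclusion to major deviations that occur at or before birth. Leave the eligibility, randomized-product and 14-day criteria as they are.
- State that infants with a later major deviation, including the events that the estimand already names, stay in the set. Their cases and follow-up before the deviation count, and observations are censored from the deviation date.
- If protocol Section 9.2 means some postnatal infant deviations to exclude, list them in Section 4 with the date from which they apply, and make the estimand text agree.

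The cost is a sentence or two in Section 4 and a deviation-date flag in the analysis data. No new data are needed.
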